6.4.3.2 Sample Collection, Storage, and Shipping

Complete details for sample collection, storage, and shipping to the central laboratory are included in the Laboratory Manual.

6.4.4 Electrocardiogram

A standard 12-lead ECG will be obtained. Subjects should rest in the supine position before each 12-lead ECG recording is started. The ECGs should be reviewed, signed, and dated by a qualified health care practitioner and any clinically important finding recorded on the ECG report and on the appropriate eCRF. The investigator is responsible for providing the interpretation of all ECGs.

6.4.5 Concomitant Medication Use

Concomitant treatment is permitted if the medication is not expected to interfere with the evaluation of safety or efficacy of the study drug. During the study, if the use of any concomitant treatment becomes necessary (e.g., for treatment or prophylaxis of an AE), the treatment must be recorded on the eCRF, including the reason for treatment, generic name of the drug, dosage, route, and date of administration. Restricted and prohibited concomitant medication use is presented in [Section 5.8](#).

The use of concomitant medications will be recorded from Day 1 through the end of the Treatment period or until the time of disease progression. Details of concomitant medication use should include the name, dose, route of administration, and indication.

6.4.6 LV305 Persistence

Peripheral blood will be collected at Screening and at the following timepoints after administration of the first dose of study drug on Day 1: no sooner than Day 92 (3 months) up to 4 months; from 6 months up to 9 months; and from 1 year up to 15 months; and then yearly at no sooner than every 12 months but not more than 15 months until study closure. If all post-treatment assays are negative during the first year, then the yearly samples should be archived. Samples will be used for an assay to test for persistence of LV305.

6.4.7 Adverse Events Assessments

All subjects who receive at least 1 study injection or another study-related procedure will be considered evaluable for safety. This includes any untoward signs (including abnormal laboratory findings) or symptoms experienced by the subject from the time of enrollment until 30 days post administration of the last dose of the study drug (i.e., CMB305). Safety will be evaluated for all treated subjects using the NCI-CTCAE v.4.03 or newer. Safety assessments will be based on medical review of both solicited and spontaneously reported AEs, including symptoms, physical examination findings, vital signs, laboratory findings, ECGs, and treatment discontinuations due to AEs. The nature, severity, and frequency of AEs will be monitored on an ongoing basis for risk assessment and to determine if risk management interventions are warranted (e.g., expedited notification of safety findings to investigators, IRBs/IECs, or regulators; update of Investigator's Brochure and ICF risks and re-consenting study subjects; revision of safety monitoring procedures; revision of eligibility criteria or other study procedures).

6.4.7.1 Adverse Event Collection Period

All enrolled subjects will have periodic assessment of clinical and laboratory AEs. All AEs, SAEs, and MEOIs will be collected until at least 30 days after administration of the last dose of the study drug (i.e., CMB305). MEOIs, immune-mediated events and secondary malignancies (regardless of causality) to be reported through 90 days following last IP dose/cessation of treatment or 30 days after initiation of new anti-cancer therapy, whichever is earlier, need to be reported to the Sponsor within 24 hours of event in the same manner as outlined for SAEs. All SAEs and new malignancies that come to the attention of the site staff and are considered at least possibly related to CMB305 will be collected until the time of last subject contact. AEs are to be reported 30 days after last dose of study drug if possibly related to CMB305/blinded IP, unless they fall in category above.

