- ⁱ For FCBP, serum and confirmation urine pregnancy testing will be performed by the local laboratory prior to dosing on Day 1; results must be negative. Serum pregnancy testing will be performed by the local laboratory prior to dosing on Day 92; results must be negative. Pregnancy testing will be performed more frequently as required per local regulatory authority.
- ^j Vital sign measurements will include body temperature, heart rate, respiratory rate, and resting systolic and diastolic blood pressure. On the day of each dosing, vital signs will be obtained no more than 60 minutes before dosing and 30 minutes after dosing (± 10 -minute window).
- ^k Once the Screening physical examination has been conducted, a simple symptom-directed physical examination should be performed for all subsequent visits. Measurements of body weight will be obtained at every visit.
- ^l Beginning in the Treatment period, imaging will be performed at 8-week intervals after Day 1 administration of the first dose of the study drug for up to 1 year or until the time investigator-determined progressive disease, using RECIST v1.1, is documented.
- ^m QoL assessments will be conducted at the study site. In addition to the screening QoL assessment, the QoL assessment will be obtained on Day 1 prior to the first dose of study drug, at Day 92, and at 6 months and 12 months after Day 1. All subjects, regardless of their disease response status, will continue to have QoL assessments performed for 12 months after Day 1.
- ⁿ All AEs and SAEs will be collected until 30 days after administration of the last dose of the study drug. Information on any SAEs and new malignancies that come to the attention of the site staff that are considered at least possibly related to CMB305 will be collected until the time of last subject contact.
- ^o After Day 92, G305 or placebo will be given on Day 148 and at 8-week intervals as a boost for up to 1 year, or until unacceptable toxicity, or investigator-determined progressive disease, using RECIST v1.1, is documented, whichever occurs first. AEs will be reported at the subsequent visit and until at least 30 days after the last dose.

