5.3 Selection and Timing of Dose for Each Subject

The CMB305 or matching placebo dosing regimen is presented in Figure 3. The proposed CMB305 regimen for this study consists of 4×10^{10} vg of LV305 (administered SC as 4 injections of 1×10^{10} vg, with one injection preferably given to each upper arm and each upper leg at each visit) on Days 1 and 22. On Day 36 (2 weeks after Day 22) the boost, G305, will be administered. Thereafter, alternating doses of LV305 and G305 will be administered every 2 weeks until Day 92. In total, 4 doses (16 SC injections) of LV305 and 3 doses (3 IM injections) of G305 will be administered through Day 92. G305 will then be administered IM at 8-week intervals for up to 1 year or until the time investigator-determined PD (using RECIST v1.1) is documented or unacceptable toxicity occurs, whichever occurs first. Details on the preparation and administration are provided in the Pharmacy Manual.

Figure 3 CMB305 or Matching Placebo Dosing Regimen

IM = intramuscular; Q8W = every 8 weeks; SC = subcutaneous

LV305 or matching placebo is administered as 4 separate 1-mL SC, each preferably administered in a separate upper or lower limb (or stump if the subject has had a resection), or administered at least 3 cm from the neighboring injection site if on the same limb/stump. G305 or matching placebo is administered IM.

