6.4.7.5 Definitions of Adverse Event

Adverse Event (AE)—Any untoward medical occurrence in a subject or clinical investigation subject administered a pharmaceutical product, medical treatment, or procedure, and which does not necessarily have to have a causal relationship with this regimen. An AE can therefore be any unfavorable and unintended sign (including an abnormal laboratory finding, for example), symptom, or disease temporally associated with the use of a medicinal product, medical

treatment, or procedure whether or not considered possibly, probably, or definitely related to the medicinal product. Progression of cancer is not considered an AE unless it is considered to be drug-related by the investigator.

Treatment-Emergent Adverse Event (TEAE)—Any AE that occurs, or an existing condition that worsens in severity, after administration of the first dose of the study drug.

Medical Event of Interest (MEOI)—Selected non-serious AEs are classified as MEOIs. The following treatment-emergent immune-mediated event is an MEOI for CMB305:

- Pneumonitis

As NY-ESO-1 is only detected in certain testicular cells in healthy individuals ([Gnjatic 2006](#)), the following male genitourinary-related events are MEOIs for CMB305:

- Prostatic pain
- Groin pain
- Testicular pain
- Epididymo-orchitis

MEOIs for this study include the following:

- An overdose of the sponsor's investigational product that is not associated with clinical symptoms or abnormal laboratory results
- Results from protocol-specified or unscheduled laboratory results showing simultaneous:
 - Increased ALT and/or AST $\geq 3 \times$ ULN,
 - Increased serum total bilirubin $\geq 2 \times$ ULN, without initial findings of cholestasis (elevated serum alkaline phosphatase) and
 - No other reason can be found to explain the combination of increased aminotransferase enzymes and total bilirubin, such as viral hepatitis A, B, or C; preexisting or acute liver disease; or another drug capable of causing the observed injury.

Note: These criteria are based upon available regulatory guidance documents.

The purpose of these criteria is to specify a threshold of abnormal hepatic test results that may require an additional evaluation for an underlying etiology. The site guidance for assessment and follow-up of these criteria can be found in the Investigator Trial File Binder (or equivalent).

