## **5.2 Safety Endpoints**

### **5.2.1 Adverse Events**

A treatment-emergent adverse event (TEAE) is defined as any AE that newly appeared or worsened in severity following initiation of the study treatment administration until 30 days after last dose of the study treatment. In addition, all study treatment related AEs are treated as TEAE.

Medical Event of Interest (MEOI) is defined as selected non-serious AEs are classified as MEOIs, refer to protocol section 6.4.7.5 for more details.

Immune-mediated event --

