### 8.3.1 Adverse Events

The verbatim terms used in the eCRF by investigators to identify adverse events will be coded to a system organ class (SOC) and a preferred term (PT) using the current Medical Dictionary for Regulatory Activities (MedDRA) version 21.0 or higher. The severity of adverse events is assessed in National Cancer Institute (NCI) common toxicity criteria for adverse events (CTCAE) Version 4.03 or higher. Only TEAEs occurring from the time of the first dose through 30 days after the last dose of the study drug and medical events of interest, immune-mediated events and related AEs will be summarized, while all AEs captured in eCRF will be listed in data listings.

TEAE will be summarized by system SOC and PT, by severity, by relationship to study treatment, and by action taken. Tables will be sorted by frequency in incidence (the highest to lowest incidence in total column).

The following TEAEs will be tabulated and organized as follows:

- Overall Summary of Treatment Emergent Adverse Events
- TEAEs by system organ class and preferred term
- TEAEs by system organ class, preferred term and worst NCI CTCAE grade
- Severe TEAEs (Grade 3 or higher) by system organ class and preferred term
- SAEs by system organ class and preferred term and worst NCI CTCAE grade
- Related TEAEs by system organ class and preferred term
- Related SAEs by system organ class and preferred term
- Related TEAEs by system organ class, preferred term and worst NCI CTCAE grade
- Related SAEs by system organ class and preferred term and worst NCI CTCAE grade
- TEAEs leading to treatment discontinuation by system organ class and preferred term
- Related TEAEs leading to treatment discontinuation by system organ class and preferred term
- TEAEs classified as Medical Event of Interest (MEOI) by system organ class and preferred term
- TEAEs resulting in death by system organ class and preferred term

TEAEs will be summarized by presenting the number and percentage of subjects having at least one TEAE in each system organ class and preferred term. A subject with multiple occurrences of the same TEAE will be counted only once in the AE category.

Separate TEAE summaries will be presented by system organ class, preferred term, and maximum CTCAE (4.03 or higher) grade. A subject with multiple CTCAE grades for the same TEAE will be summarized under the maximum CTCAE grade recorded for the event.

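### In the Boost phase the 30-day adverse event window is shorter than the 56-day dosing interval, so an unrelated event 31 to 56 days after a boost is tabulated only if another boost follows

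*Protocol*

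**What the plan says.** **Dosing.** In the Prime phase, doses fall on Days 1, 22, 36, 50, 64, 78 and 92. For the Boost phase, protocol Table 2 footnote o says: "After Day 92, G305 or placebo will be given on Day 148 and at 8-week intervals as a boost for up to 1 year".

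**Collection.** Protocol 6.4.7.1 sets a minimum: "All AEs, SAEs, and MEOIs will be collected until at least 30 days after administration of the last dose of the study drug". Table 2 footnote n gives the same limit without the words that make it a minimum: "All AEs and SAEs will be collected until 30 days after administration of the last dose of the study drug". Protocol 6.4.7.3 requires any new SAE to be recorded up to 30 days after the last dose, and after that only events that may be causally related.

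**Analysis.** SAP 5.2.1 defines a TEAE as an event that is new or worse "following initiation of the study treatment administration until 30 days after last dose of the study treatment", and adds treatment-related events with no time limit. SAP 8.3.1 summarizes only TEAEs inside that window, plus MEOIs, immune-mediated events and related events. All other captured events go to listings. One of the planned tables is "TEAEs leading to treatment discontinuation by system organ class and preferred term"; others cover SAEs and TEAEs resulting in death.

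**A second definition.** Protocol 6.4.7.5 defines a TEAE with no end date: "Any AE that occurs, or an existing condition that worsens in severity, after administration of the first dose of the study drug".

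**The concern.** Between boosts a subject is still in the Treatment period, waiting for the next dose. From day 31 to day 56 after a boost, whether an unrelated event counts depends on something that happens later: whether another dose moves the last-dose date forward. An event that itself prevents the next dose, or is fatal, cannot meet that condition. So the rule can drop an event from the tables because of the event's own consequence, and the tables exposed are those for discontinuation, death and SAEs.

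After day 30, inclusion also rests on the investigator's causality judgement, which an all-cause TEAE table is meant to avoid. No passage explains why the general window is shorter than the boost interval.

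**Working it through.** **1. Schedule.** 92 + 56 = Day 148, which matches footnote o. Further boosts fall on Days 204, 260 and 316. The next would be Day 372, beyond 1 year.

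**2. Prime phase.** The gaps are 21, 14, 14, 14, 14 and 14 days. All are under 30, so there is no hole.

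**3. Boost phase.** 56 − 30 = 26 days (days 31 to 56), and 26/56 = 46% of an interval. Leaving out the day of the next dose gives 25 days (45%). If the ±7-day visit window is applied to the gap since the previous boost, the gap is 49 to 63 days and the uncovered part is 49 − 30 = 19 to 63 − 30 = 33 days.

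**4. Calendar.** From Day 92 to Day 365 there are 365 − 92 + 1 = 274 days. Of these, 4 × 25 + 19 = 119 (43%) lie more than 30 days after the most recent dose. They are lost only when no later dose follows.

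**5. Completer.** The last boost is on Day 316 and the window closes on Day 316 + 30 = Day 346. 365 − 346 = 19 days of the Treatment period remain.

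**6. One event, two outcomes.** Take an unrelated SAE, neither MEOI nor immune-mediated, starting 40 days after the Day 204 boost (Day 244).
- If the Day 260 boost is given, the window runs to at least Day 260 + 30 = Day 290. The event is a TEAE.
- If treatment stops on Day 244, the last dose was Day 204 and the window closed on Day 204 + 30 = Day 234. The event is not a TEAE under SAP 5.2.1. It appears only in listings, if the site recorded it.

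**7. Can the loss be sized?** Assumptions that are not in the documents: exponential PFS and treatment ending only at progression. The medians are the design values, 4 months on placebo and 4/0.55 = 7.3 months on CMB305, with 30.4375 days per month (SAP 7.1). With S(t) = 0.5^(t/median), the share of stops before 1 year that fall more than 30 days after the last dose is:

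| When progression ends treatment | Placebo | CMB305 |
|---|---|---|
| Any day | 22% | 28% |
| At scans every 56 days from Day 1 (Days 57, 113, 169, 225, 281, 337) | 0% | 0% |
| At scans on Day 64 and at boost visits | 0.529/0.835 = 63% | 0.447/0.628 = 71% |

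The second row is zero because each Boost-phase scan falls 21 days after a boost (113 − 92 = 21). Protocol 3.1.3 and 6.3.1.3 support that row. The imaging marks in Table 2, at Day 64 and the Boost visits, can be read as the third.

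The ordering of the arms also depends on the denominator. Per randomized subject, the any-day model gives 19.7% on placebo and 18.7% on CMB305, and the boost-visit model gives 53% and 45%. All these figures count progression-driven stops, and under protocol 6.4.7.5 progression is not an adverse event unless judged drug-related. No adverse event rate enters, so no count of lost events follows.

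**The case against.** The strongest reply is that the exceptions cover most of what matters.
- SAP 5.2.1 keeps related events as TEAEs at any time, and SAP 8.3.1 also summarizes MEOIs and immune-mediated events. Protocol 6.4.7.1 has MEOIs, immune-mediated events and secondary malignancies reported to 90 days, or to 30 days after new anti-cancer therapy if that is earlier.
- The discontinuation criteria in protocol 5.6.3 concern drug-related events, which stay in the tables.
- Collection does not simply stop on day 30. Section 6.4.7.1 gives a minimum, 6.4.7.2 has sites ask about events at every visit, and footnote o says "AEs will be reported at the subsequent visit and until at least 30 days after the last dose".
- Deaths are still captured through the OS endpoint. Protocol 7.8 also plans summaries of events leading to withdrawal, SAEs and deaths without stating a TEAE limit on them.

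Most of this stands, and it rules out several stronger readings. A reader might infer that every event on days 31 to 56 counts only if the subject is dosed again, or that the rule removes exactly the events that end treatment. Related events, MEOIs and immune-mediated events contradict both. A reader might also infer that 46% of Boost-phase events are lost, or that the arm treated longer is made to look safer. The 46% is a share of days after a final boost, and step 7 shows that the size and direction of any difference between arms change with the scan schedule and the denominator.

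The reply does not remove the gap. Protocol 6.5.2 also lets the investigator stop dosing for any other reason judged to be in the subject's interest, so an unrelated event can end treatment. A death counted in OS does not put the fatal event in the TEAE table. SAP section 9 says the SAP prevails over the protocol's analysis text, so the narrower rule governs. The immune-mediated exception is also weak in the SAP, where section 5.2.1 leaves that definition blank.

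**Conclusion.** The concern holds in a limited form. It applies to events judged unrelated that are neither MEOIs nor immune-mediated, including unrelated SAEs and fatal events, with onset more than 30 days after what proves to be the last boost. For these, TEAE status depends on whether another boost is given.

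The exposure is up to 26 of the 56 days after a final boost, and about 19 days for a completer on the nominal schedule. Both figures follow from the dosing schedule alone. The number of events affected, and whether the arms are affected differently, cannot be derived: they depend on adverse event rates and on whether scans fall at boost visits. The problem is mainly one of tabulation, with a secondary gap in required collection because footnote n and 6.4.7.3 can be read as a fixed 30-day stop.

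**What to change.** In SAP 5.2.1 and 8.3.1, and in protocol 6.4.7.1, 6.4.7.3, 7.8 and Table 2 footnote n:
- End general adverse event collection and the TEAE window at the later of 30 days after the last dose and the documented date on which study treatment is discontinued or completed.
- Count as a TEAE, whatever its causality, any event recorded as the reason for stopping study drug or that is fatal before that date.
- Align the open-ended TEAE definition in protocol 6.4.7.5 with this rule.

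The cost is wording. Subjects on treatment are already seen every 8 weeks in the Boost phase, so no visits are added. A few more unrelated events will be tabulated. The post-dose window will vary between subjects: a completer on Day 365 would have 365 − 316 = 49 days, while a subject whose stop is documented 21 days after a boost would have 30. An exposure-adjusted summary of event rates by arm would deal with that.

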6.4.7.2 Adverse Event Reporting

All SAEs that are unexpected and considered possibly, probably, or definitely related to study drug by the investigator or sponsor will be reported to the Food and Drug Administration (FDA), applicable regulatory agencies, and IRB/IEC in accordance with the requirements in 21 Code of Federal Regulations (CFR) §312.32 and International Conference on Harmonization (ICH) guidelines.

At each study visit (including unscheduled visits), the investigator, or designee, will determine whether any AEs have occurred. Each AE will be reported in the subject's medical record and on the AE eCRF page and classified according to the criteria in [Section 6.4.7.4](#), [Section 6.4.7.6](#), and [Section 6.4.7.7](#). If known, the diagnosis should be recorded, in preference to the listing of individual signs and symptoms. Any pre-existing conditions that are detected as part of the initial screening procedures will be reported in the medical history and not as an AE. However, pre-existing conditions that worsen after enrollment should be reported as an AE.

Adverse events will be reported to the FDA and applicable regulatory authorities in accordance with the requirements outlined in 21 CFR §312.32 and ICH guidelines. Progression of cancer is not considered an AE unless it is considered to be drug-related by the investigator. Deaths due to cancer progression will not be reported as expedited events. The investigator will continue to monitor the subject until any new, changed, or worsened AE resolves, returns to baseline, or until the investigator and IMDZ agree that follow-up is no longer necessary. AEs must be followed until resolution whenever possible.

6.4.7.3 Serious Adverse Event Reporting

If an SAE occurs, IMDZ will be notified within 24 hours of awareness of the event by the investigator. In particular, if the SAE is fatal or life-threatening, IMDZ must be notified immediately, irrespective of the extent of available AE information. In the rare event that the investigator or designee does not become aware of the occurrence of an SAE immediately, the investigator or designee must report the event within 24 hours of their awareness and document the time of when his/her first awareness occurred. For all SAEs, the investigator or designee is obligated to pursue and provide information to IMDZ in accordance with the time frames for reporting specified above. In addition, an investigator may be requested to obtain specific additional follow-up information in an expedited fashion. This information may be more detailed than that captured on the AE case report form. In general, this will include a description of the AE in sufficient detail to allow for a complete medical assessment of the case and independent determination of causality.

New SAEs experienced by subjects during the Screening period (pre-study treatment) will be reported to IMDZ if the events are considered related to study procedures. New SAEs determined to be related to study tests or procedures (not including cancer-related events) and any hospitalizations determined to be related to study tests or procedures that are experienced by subjects from the time of signing the Main Study ICF/assent form until Day 1 (start of CMB305

treatment) will be noted on the SAE form and eCRF. From Day 1 until 30 days after administration of the last dose of the investigational product (i.e., CMB305), any new SAE will be noted on the SAE form and eCRF. After that point, any AE that comes to the attention of the site staff that may be causally related to study drug, i.e., CMB305, (i.e., there is a reasonable possibility that the event may have been caused by the drug) will be reported to IMDZ.

SAEs will be monitored until they have resolved, returned to baseline, or they are not clinically significant, stable, or do not require additional follow-up, as judged by the investigator and IMDZ.

STUDY CONTACT FOR REPORTING SERIOUS ADVERSE EVENTS	
Vendor:	Everest Clinical Research, Corp.
Telephone:	PPD [REDACTED] (office) or PPD [REDACTED] (mobile)
